## 10.2 Secondary Endpoint Analyses

All other statistical analyses will be descriptive in nature. Exploratory comparisons may be made between treatment arms of the randomized population. For all analyses of the combined population each treatment arm will be analyzed separately. In general, summary statistics (n, mean, standard deviation, median, minimum, and maximum for continuous variables, and number of subjects and percentage in each category for categorical variables) will be provided. Time to event variables will be summarized using Kaplan-Meier curves, and their medians will be estimated using the Kaplan-Meier method.

Additionally, source data for summaries will be presented as subject data listings. The details for analyses will be specified in the SAP.

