- Time to first SRE (defined as time to EBRT, time to first pathological bone fracture, time to spinal cord compression and time to surgical intervention) was statistically significantly longer in the radium-223 chloride group compared to placebo (median number of months = 15.6 for radium-223 chloride versus 9.8 months for placebo [HR = 0.658, 95% CI: 0.522, 0.830, p = 0.00037]).
- Time to total ALP progression (defined as  $\geq 25\%$  increase compared to baseline / nadir) was statistically significantly longer in the radium-223 chloride group, 7.4 months compared to 3.8 months in the placebo group (HR = 0.167, 95% CI: 0.129, 0.217; p < 0.00001).
- Time to PSA progression (defined as a  $\geq 25\%$  increase and an increase in absolute value of  $\geq 2$  ng/mL compared to baseline/nadir) was also significantly prolonged in patients receiving Radium Ra 223 dichloride compared to patients receiving placebo (HR = 0.643, 95% CI: 0.539, 0.768; p < 0.00001).
- A total ALP response (defined as a confirmed  $\geq 30\%$  or  $\geq 50\%$  reduction compared to baseline) at week 12 was observed in higher proportions of subjects who were treated with radium-223 chloride group (47% and 3% respectively) compared to those in the placebo group (3% and < 1% respectively).
- Subgroup survival analysis showed a consistent survival benefit for treatment with Radium Ra 223 dichloride, independent of total alkaline phosphatase, current use of bisphosphonates, prior use of docetaxel and baseline ECOG status. The results from the phase III ALSYMCA study regarding time to external beam radiation therapy (EBRT) for pain relief and fewer patients reporting bone pain as an adverse event in the Radium Ra 223 dichloride group indicate a positive effect on bone pain.

The most common adverse reactions ( $\geq 10\%$ ) in patients receiving Radium Ra 223 dichloride were nausea, diarrhea, vomiting, and peripheral edema (Table 3). Grade 3 and 4 adverse events were reported among 57% of Radium Ra 223 dichloride-treated patients and 63% of placebo-treated patients. The most common hematologic laboratory abnormalities in Radium Ra 223 dichloride-treated patients ( $\geq 10\%$ ) were anemia, lymphocytopenia, leukopenia, thrombocytopenia, and neutropenia (Table 4). Treatment discontinuations due to adverse events occurred in 17% of patients who received Radium Ra 223 dichloride and 21% of patients who received placebo.

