#### 4.4 Duration

It is expected that all patients will be accrued within 18 months. Subjects will remain on study treatment for up to 6 months. Patients will be followed for a total of two years from the first day of protocol treatment or until death, whichever occurs earlier. The total study duration for a patient is expected to be 2 years from the time of enrollment.

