### Secondary and Exploratory Variables

The exploratory variables include:

- rPFS
- Time to radiological bone progression
- Total ALP response rate
- Time to total ALP progression
- Percentage change in total ALP
- PSA response rate
- Time to PSA progression
- Time to first skeletal related event (as defined below)
- OS for 2 years after enrollment
- Percent change in opioid requirement (in morphine equivalent) during protocol treatment.

Skeletal related events include the following:

- Time to occurrence of first use of external beam radiotherapy to relieve skeletal symptoms
- Time to occurrence of first tumor related orthopedic surgical intervention
- Time to occurrence of first spinal cord compression
- Time to occurrence of first new symptomatic pathological bone fractures (vertebral and non-vertebral)

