### 10.3 Exploratory Analyses

Exploratory analyses will be performed on the combined population. For additional exploratory purposes, Kaplan-Meier curves and estimates will be presented for time to event variables (rPFS, time to radiological bone progression, time to total ALP progression, time to PSA progression, OS, time to first SRE).

Frequencies and percentages will be provided for categorical variables (total ALP response rate, PSA response rate, pain response rate). Summary statistics (n, mean, standard deviation, median, minimum, and maximum) will be presented for continuous variables (percentage change in total ALP).

Further details, including handling missing data and additional censoring details, will be described in the SAP.

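### Time to first skeletal related event (SRE) is summarized only by Kaplan-Meier, death before an SRE is not addressed, and a cumulative incidence with death as a competing event should be added

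*Combined protocol and SAP*

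**What the plan says.** Section 1.2.3 lists time to first SRE among the secondary objectives to be compared between arms. Section 10.2 covers all time-to-event variables with one sentence: "Time to event variables will be summarized using Kaplan-Meier curves, and their medians will be estimated using the Kaplan-Meier method". Section 10.3 repeats the method and names the variables, among them "time to total ALP progression, time to PSA progression, OS, time to first SRE".

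The list of secondary and exploratory variables in Section 10.2 defines an SRE by four components: external beam radiotherapy for skeletal symptoms, tumor-related orthopedic surgery, spinal cord compression, and new symptomatic pathological fracture. Death is not among them. No competing-risk or cumulative incidence method appears in the document.

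On censoring, Section 10.3 says only this: "Further details, including handling missing data and additional censoring details, will be described in the SAP". The text supplied contains no such detail for SREs. On the status of these results, Section 10.2 says: "All other statistical analyses will be descriptive in nature".

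**The concern.** A man who dies without an SRE can no longer have one. If he is censored at death, Kaplan-Meier treats him as if he shared the later SRE risk of the men still alive. The resulting curve answers a hypothetical question: when would SREs occur if nobody died first? Read as the share of patients who have an SRE, one minus Kaplan-Meier is too high whenever deaths precede later SREs. The direction follows from how the estimator is built; only the size depends on assumptions.

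Mortality over the follow-up period may be substantial. Section 4.4 says: "Patients will be followed for a total of two years from the first day of protocol treatment or until death, whichever occurs earlier". The trials cited in the background report median overall survival of 14.9 months with radium-223 (Section 3.1.4) and 18.4 months with enzalutamide (Section 2.1). With constant hazards these imply about 67% and 60% mortality by 24 months. At stake is the reading of a secondary result: a reported median time to SRE may suggest that half the patients have an SRE by then, when fewer do.

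**Working it through.** The plan states no SRE risk, event count or power, so there is no figure to reproduce. What follows is an illustration, not a forecast for this trial.

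**Inputs**
- SRE medians in the cited phase III radium-223 trial, Section 3.1.4: "median number of months = 15.6 for radium-223 chloride versus 9.8 months for placebo". I take these as medians of the SRE hazard with death censored, which is an assumption.
- Overall survival medians: 14.9 months (radium-223) and 11.3 months (placebo), Section 3.1.4; 18.4 months (enzalutamide after docetaxel), Section 2.1.
- Horizon: 24 months, Section 4.4.
- Assumption: constant, independent hazards, each equal to ln 2 / median.

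**Formulas**, with s the SRE hazard and d the hazard of death before an SRE
- One minus Kaplan-Meier, death censored: 1 − exp(−24s)
- Cumulative incidence, death competing: s/(s+d) × [1 − exp(−24(s+d))]
- Plateau of the cumulative incidence: s/(s+d)

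**Main case: SRE 15.6 months, overall survival 14.9 months**
- s = 0.6931/15.6 = 0.04443; d = 0.6931/14.9 = 0.04652; s+d = 0.09095
- One minus Kaplan-Meier: 1 − exp(−1.0664) = 65.6%
- Plateau: 0.04443/0.09095 = 48.9%
- Cumulative incidence: 0.4885 × [1 − exp(−2.1829)] = 0.4885 × 0.8873 = 43.3%
- Excess: 22.2 points, before rounding

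The planned median is affected as well. Kaplan-Meier gives 15.6 months, while the cumulative incidence levels off below 50% and has no median. In 4,000 simulated trials with 27 patients and complete 24-month follow-up, a Kaplan-Meier median was reached in 88% of runs, but the observed cumulative incidence reached 50% in only 24%.

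**Sensitivity to deaths before an SRE.** Overall survival also counts deaths after an SRE, so using the whole death hazard as d is an upper case. The table scales d down. Each cell gives the 24-month cumulative incidence, with the excess of one minus Kaplan-Meier in points in brackets.

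| Share of overall death hazard acting before an SRE | SRE 15.6, OS 14.9 (1−KM 65.6%) | SRE 15.6, OS 18.4 (1−KM 65.6%) | SRE 9.8, OS 11.3 (1−KM 81.7%) |
|---|---|---|---|
| 100% | 43.3% (22.2) | 46.6% (19.0) | 51.3% (30.4) |
| 75% | 47.7% (17.9) | 50.4% (15.1) | 56.9% (24.8) |
| 50% | 52.7% (12.9) | 54.8% (10.7) | 63.6% (18.1) |
| 25% | 58.6% (7.0) | 59.9% (5.7) | 71.8% (9.9) |

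At shares of 25% to 75% the excess is 5.7 to 24.8 points. The top of that range comes from the placebo pair; the other two pairs give 5.7 to 17.9 points. In the first column at a 50% share, the cumulative incidence reaches 50% at 21.2 months, against a Kaplan-Meier median of 15.6.

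**The case against.** The strongest reply is that the plan makes no error here. Kaplan-Meier with death censored is a recognized summary of the cause-specific SRE hazard, the plan is silent on death because it defers censoring details, and the results are descriptive. Most of this stands, and it rules out several stronger readings.

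- **A reader might infer that the trial will report an overstated two-year SRE risk.** No such estimate is planned. Sections 10.2 and 10.3 promise curves, estimates and medians, and the only two-year item in the variable list is overall survival. The overstatement arises when the curve or median is read as an actual probability or time.
- **A reader might infer that the plan prescribes censoring at death.** It does not say so. This is the usual default, and it is inferred.
- **A reader might infer that Kaplan-Meier distorts the comparison between arms.** The figures do not show that. Give both arms an SRE median of 15.6 months and let median survival be 14.9 in one and 18.4 in the other. Kaplan-Meier gives 65.6% in both, correctly showing equal SRE hazards. Cumulative incidence gives 43.3% and 46.6%, so the arm with more deaths appears to have fewer SREs. The two summaries answer different questions, and either can mislead alone.
- **A reader might take the 22-point gap as the expected size.** It uses the whole survival hazard from other populations. The enzalutamide trial was entirely post-docetaxel with 23% visceral disease (Section 3.2.2); this trial excludes visceral metastases and admits men who declined docetaxel. Mortality before an SRE is not given for this trial.

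Precision is also poor: with 12 controls, a simple 95% margin around 66% is 1.96 × √(0.66 × 0.34/12), about 27 points. That limits what either estimate can show, but imprecision does not remove a systematic difference between them.

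The reply does not dispose of the median. It is a planned output, and it can be reported as reached when fewer than half the patients ever have an SRE. Deferred censoring rules would not by themselves supply a cumulative incidence.

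**Conclusion.** The point holds as a cheap improvement to a secondary, descriptive analysis. Kaplan-Meier is the only method named for time to first SRE, and death before an SRE is not addressed. If those deaths are censored, the reported curve and median overstate the SRE probability patients face. The illustrated excess at 24 months is about 6 to 25 points when a quarter to three quarters of the death hazard acts before an SRE. It is 22 points in the main case with the full hazard. These sizes rest on constant, independent hazards and on medians from other trials; the direction does not. Nothing here touches the N-telopeptide analysis, the safety test, or any error rate.

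The 24-month horizon is itself uncertain. Section 6.6 lists disease progression among the reasons for mandatory withdrawal, during both treatment and follow-up. Section 9.2 names time to first skeletal event next to two-year follow-up, Section 4.4 follows patients for two years, and Section 9.4.1 continues follow-up for overall survival regardless of progression. If SRE collection stops at progression, fewer deaths compete within the observed time, and informative censoring at progression becomes the larger concern. A cumulative incidence estimate would not cure that.

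**What to change.** In Sections 10.2 and 10.3:

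1. State how a death before a first SRE is handled.
2. Report the Aalen-Johansen cumulative incidence of first SRE by arm, with death as a competing event, alongside the Kaplan-Meier summary. Label the latter as cause-specific.
3. Optionally add SRE-free survival (first of SRE or death) by Kaplan-Meier, for which a median has its ordinary meaning.
4. Say in one sentence that the summaries answer different questions: the Kaplan-Meier summary concerns the rate of SREs among men still alive and SRE-free, and the cumulative incidence concerns the share of patients who have an SRE.
5. Reconcile Sections 4.4, 6.6, 9.2 and 9.4.1 on how long SREs are collected, and state the censoring time for patients whose SRE collection ends before death.

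The cost is one more analysis output. Deaths are already collected for overall survival, so the competing event needs no new data. The cumulative incidence is less directly comparable with published Kaplan-Meier SRE medians, which is a reason to keep the Kaplan-Meier summary beside it.

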### Secondary and Exploratory Variables

The exploratory variables include:

- rPFS
- Time to radiological bone progression
- Total ALP response rate
- Time to total ALP progression
- Percentage change in total ALP
- PSA response rate
- Time to PSA progression
- Time to first skeletal related event (as defined below)
- OS for 2 years after enrollment
- Percent change in opioid requirement (in morphine equivalent) during protocol treatment.

Skeletal related events include the following:

- Time to occurrence of first use of external beam radiotherapy to relieve skeletal symptoms
- Time to occurrence of first tumor related orthopedic surgical intervention
- Time to occurrence of first spinal cord compression
- Time to occurrence of first new symptomatic pathological bone fractures (vertebral and non-vertebral)

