### 1.2 Secondary Objectives and Endpoint

To compare the following objectives between the two arms:

- 1.2.1 Time to progression in serum prostate-specific antigen (PSA), total alkaline phosphatase (ALP) concentrations, and radiological progression.
- 1.2.2 Response rates by serum PSA and total ALP concentrations.
- 1.2.3 Time to first skeletal related event.
- 1.2.4 Percent change in opioid use (morphine equivalent) during protocol treatment.
- 1.2.5 Overall Survival at 2 years post enrollment.

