- 5.1.8**  Symptomatic Bone metastases.
- 5.1.9**  Adequate hematologic, renal, and liver function as evidenced by the following:
1. White blood cell (WBC)  $\geq$  3,000 cells/ $\mu$ L
  2. Absolute neutrophil count (ANC)  $\geq$  1,500 cells/ $\mu$ L
  3. Platelet Count  $\geq$  100,000 cells/ $\mu$ L
  4. Hemoglobin (HgB)  $\geq$  10.0 g/dL
  5. Total Bilirubin  $\leq$  1.5 x upper limit of normal (ULN)
  6. Creatinine  $\leq$  1.5 X ULN
  7. Aspartate aminotransaminase (AST, SGOT)  $\leq$  2.5 x ULN
  8. Alanine aminotransaminase (ALT, SGPT)  $\leq$  2.5 x ULN
  9. Albumin  $>$  25 g/L
  10. Creatinine clearance  $>$  30ml/min
- Transfusion of blood products are not allowed to normalize blood parameters within 4 weeks of the first Radium treatment.
- 5.1.10**  Men must agree to use adequate contraception beginning at the signing of the ICF until at least 6 months after the last dose of study drug. Because of the potential side effect on spermatogenesis associated with radiation, men who are sexually active must agree to use condoms and their female partners of reproductive potential must agree to use a highly effective contraceptive method during and for 6 months after completing treatment.
- 5.1.11**  Able to provide informed consent and have signed an approved consent form that conforms to federal and institutional guidelines to ensure compliance with HIPAA regulations.

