### **6.5 Concomitant Medications**

All medication that is considered necessary for the subject’s welfare, and which is not expected to interfere with the evaluation of the study treatment, may be given at the discretion of the investigator. Collection of opioid-use in morphine equivalent will be captured on the case report forms

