### Randomization

A total of 39 patients will be randomized, 27 patients to the enzalutamide + radium-223 arm and 12 patients to the control enzalutamide only arm. The Research Compliance Office will randomize patients and maintain the randomization table for this trial.

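### The opioid endpoint is stated only as percent change, which has no value at a zero baseline, so baseline non-users, including those who start opioids on study, contribute nothing under per-patient summaries

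*Combined protocol and SAP*

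**What the plan says.** Objective 1.2.4 reads "Percent change in opioid use (morphine equivalent) during protocol treatment", under a lead-in that calls for comparing the two arms. The study summary repeats it as the fourth secondary objective. The variable list in section 10.2 has "Percent change in opioid requirement (in morphine equivalent) during protocol treatment". None of the three places gives a formula, a baseline window, an on-treatment value or a rule for a baseline of zero.

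Other parts of the document that bear on the point:

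- **Eligibility (5.1.8)** requires "Symptomatic Bone metastases". No inclusion criterion requires opioid use. The note to 5.2.15 admits patients on stable fentanyl, so both users and non-users can enrol.
- **Data (6.5):** "Collection of opioid-use in morphine equivalent will be captured on the case report forms". No collection times are given.
- **Summaries (10.2):** in general, "summary statistics (n, mean, standard deviation, median, minimum, and maximum for continuous variables", together with per-patient listings of the source data.
- **Section 10.3:** summary statistics "will be presented for continuous variables (percentage change in total ALP"). Opioid change is not named there.
- **Deferral (10.3):** "Further details, including handling missing data and additional censoring details, will be described in the SAP". Section 10.2 likewise leaves analysis details to a SAP. The supplied document contains no further SAP text on this endpoint.
- **Populations:** "A total of 39 patients will be randomized, 27 patients to the enzalutamide + radium-223 arm and 12 patients to the control enzalutamide only arm". The analysis-sets paragraph assigns secondary and exploratory analyses to the combined population, which adds the 8 patients enrolled before randomization (35 combination and 12 control planned).

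**The concern.** Percent change divides by the baseline. A patient who takes no opioids at entry has no percent change, whether he stays at zero or goes to a high dose. Those who start opioids on study are a group in whom a treatment difference in opioid need could appear, and the stated metric has no place for them. Section 2.1 hypothesises that the combination will improve pain, and opioid use is the listed secondary objective closest to that claim. If the two arms differ mainly in new opioid use, the summary could show no difference. The patients who remain are also a subset selected by baseline opioid use, not the full arms.

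The scale is uneven as well. Falls stop at -100% while rises have no limit, so the same rise in dose counts very differently depending on where the patient began.

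**Working it through.** The plan gives no sample size, expected value or power for this endpoint, so there is no figure of its own to reproduce. The check is by definition and by simple counts.

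**1. The formula.** Per patient, percent change = 100 × (follow-up − baseline) / baseline. Absolute change = follow-up − baseline. The doses below are made up for illustration.

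| Baseline → follow-up (mg morphine equivalent) | Percent change | Absolute change |
|---|---|---|
| 30 → 60 | +100% | +30 |
| 30 → 15 | −50% | −15 |
| 0 → 0 | undefined | 0 |
| 0 → 60 | undefined | +60 |
| 5 → 20 | +300% | +15 |
| 100 → 115 | +15% | +15 |

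**2. How many patients have a value.** Let q be the share with zero baseline use. The documents do not give q; 20% to 60% is an assumption. Expected computable patients = n × (1 − q), with n from section 4.2 and the randomization paragraph.

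| q (assumed) | Control, n = 12 | Combination, combined population, n = 35 | Combination, randomized only, n = 27 |
|---|---|---|---|
| 20% | 9.6 | 28.0 | 21.6 |
| 40% | 7.2 | 21.0 | 16.2 |
| 60% | 4.8 | 14.0 | 10.8 |

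The control arm is 12 in either population, so it is where the loss bites hardest.

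**3. What the metric can miss.** Take 12 patients: 6 stay at 40 mg, 3 go from 0 to 40 mg, and 3 stay at 0.

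- Per-patient percent change: 6 computable values, all 0, so the mean and median are 0%.
- Mean absolute change over all 12: (3 × 40) / 12 = +10 mg.
- Baseline non-users who start: 3 of 6, or 50%.
- Percent change of the group mean: baseline mean 240/12 = 20, follow-up mean 360/12 = 30, so +50%.

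The same data give 0% or +50% depending on whether percent change is taken per patient or on the group mean, and the plan does not say which applies. The median absolute change in this example is also 0, because 9 of the 12 do not change. Absolute change alone is therefore not enough, and the proportion of new starters has to be reported beside it.

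**The case against.** The strongest reply is that nothing in the document excludes these patients. Exclusion is an inference from the formula, and analysis details are deferred to a SAP that could add a rule. That stands as a limit on the wording: a reader might infer that the plan drops non-users on purpose, and the text does not say so. It does not remove the problem. No rule is in the supplied text, and a zero baseline is an observed value, so a rule for missing data would not naturally cover it.

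Second, the per-patient reading is itself inferred. The sentence on summary statistics is general, and section 10.3 does not name opioid change. A percent change of arm means would include new starters. This is correct, but the plan specifies no such calculation, and the listed statistics (n, median, minimum, maximum) fit one value per patient.

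Third, a reader might conclude that new starters would be invisible, or that one patient with a tiny baseline would decide the result. The documents do not support either. Medians and ranges are planned alongside means, and source data are to be listed by patient, so a new start could be seen there even if it is absent from the summary.

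Fourth, it is tempting to express the loss against the 39 randomized patients. The set for secondary analyses is the combined population, with each arm analysed separately. Comparisons within the randomized population are optional and exploratory.

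Finally, the plan does not claim that opioid starts are the best sign of worsening pain. Radiotherapy for skeletal symptoms counts as a skeletal related event, and section 10.3 mentions a pain response rate, though without defining it. Other listed variables may therefore carry part of this information.

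**Conclusion.** The concern holds in a limited form. Percent change is the only stated metric, zero baselines are allowed, and under per-patient summaries baseline non-users yield no value whether or not they start opioids. This is more than a missing detail, because the chosen metric cannot represent new opioid use at all.

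The size is unknown. On the assumed 20% to 60% with no baseline use, about 5 to 10 of 12 controls and 14 to 28 of 35 combination patients would be computable (11 to 22 of the 27 randomized to that arm). The conclusion rests on that assumed share and on the per-patient reading.

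The endpoint is the fourth of five secondary objectives, is listed among the exploratory variables, and is descriptive and unpowered. A reader should not infer any effect on the N-telopeptide or safety conclusions. The change is worth making because it is cheap and the present summary could mislead on opioid need.

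**What to change.** In objective 1.2.4, the study summary and section 10.2:

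1. Define the baseline opioid value and the on-treatment value, including the window over which each is averaged, and state that change is calculated per patient.
2. Report absolute change from baseline in morphine equivalents for all patients, by arm, with the median and range. Use a rank-based method for any exploratory comparison in the randomized population.
3. Add the number and proportion of baseline non-users who start opioids during treatment, by arm.
4. Keep percent change as a description among baseline users only, and show how many patients that is.

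The cost is mostly wording. Opioid use in morphine equivalents is already to be captured on the case report forms, but no timing is stated, so someone must confirm that the entries support the chosen windows. There are two small downsides: absolute change gives more weight to high-dose users, and results compare less directly with reports that use percent change. Item 4 limits the second.
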